Study Protocol and Statistical Analysis Plan:

The impact of endoscopic surveillance of atrophic gastritis with and without intestinal metaplasia on a high-risk population for gastric cancer in Latin America: The ECHOS cohort study

NCT: not assigned

July 10, 2023

INTRODUCTION

Gastric cancer is the 5th most common cancer and the 4th leading cause of cancer-related deaths worldwide.¹ Chronic atrophic gastritis (CAG) is part of a sequential histopathological cascade that precedes the development of gastric adenocarcinoma (GA).² Chronic *Helicobacter pylori* (*H. pylori*) infection is the primary trigger of this cascade and leads to chronic inflammatory changes in the gastric mucosa which can lead to CAG, intestinal metaplasia (IM), dysplasia and eventually GA.^{3,4}

Multiple strategies have been suggested for GA prevention.⁵⁻⁸ Primary prevention is based on the recognition and treatment of *H. pylori* as the main risk factor for GA.⁹⁻¹² Secondary prevention relies on endoscopic surveillance of high-risk patients for the detection of early-stage GA with potentially curative resection. CAG and IM can be accurately identified and graded through gastric mapping biopsies obtained according to the updated Sydney System biopsy protocol (USSBP).¹³ Staging of preneoplastic conditions with Operative Link on Gastritis Assessment (OLGA) or Operative Link on Gastric Intestinal Metaplasia Assessment (OLGIM) scales¹⁴ has demonstrated to accurately predict the risk of progression to GA in some populations;¹⁵⁻¹⁸ however, the value of these systems for risk stratification has not been comprehensively evaluated in a high-risk Latin American population.

In Chile, gastric cancer is the leading cause of cancer-related deaths in men and the 3rd in females, with mortality rates of 25 and 12.2 per 100,000 inhabitants, respectively. Risk stratification of patients with CAG/IM would help with prioritization of EGDs for those with CAG/IM at highest risk of progression and minimizing endoscopic burden. However, there are limited data in Latin America regarding risk factors associated with progression of gastric preneoplasia, and specifically, the performance of OLG/OLGIM staging for risk stratification.²⁴

Accordingly, our objective was to evaluate the risk factors associated with incident high grade dysplasia (HGD)/GA in patients with CAG with or without IM who are enrolled in endoscopic surveillance, as well as to compare HGD/GA incidence according to the OLGA and OLGIM

scales. As an exploratory analysis, we also evaluated the stage of GA among those enrolled in endoscopic surveillance, given that most GA in Chile are diagnosed in the advanced stage.

METHODS

Study design and settings

The Endoscopic Cohort and Histological OLGA staging (ECHOS) study is a retrospective longitudinal cohort developed in the Pontificia Universidad Católica de Chile health care system, an open health care system with 3 endoscopic units in Santiago, Chile. Patients 18 years or older were eligible for the study if they had at least one non-urgent outpatient EGD with gastric biopsies collected following the USSBP between June 2015 and June 2021. The baseline EGD was defined as the earliest examination conducted between this time frame that met inclusion criteria. Participants were included in the cohort if they underwent a subsequent "surveillance" EGD. In order for the subsequent EGD to qualify as surveillance, it needed to occur at least 6 months after the baseline EGD and include gastric biopsies collected according to the USSBP; one exception to the USSBP requirement was if HGD or GA was detected on the surveillance (i.e. non-baseline) EGD. Patients with prior history of HGD or any type of gastric malignancy, gastrectomy or non-gastric active malignancy were excluded. Also, patients with HGD or GA on the baseline EGD were excluded. Patients with indefinite (IND) or low-grade dysplasia (LGD) on the baseline EGD were considered for the cohort (see below).

Demographic variables, medical comorbidities, and first-degree family history of gastric cancer were recorded from clinical records. The baseline and follow-up endoscopic findings were abstracted from the procedure reports, including the presence of any overt lesions or abnormalities. The baseline and follow-up histological findings, including *H. pylori* status (as defined by histologic findings), CAG and IM anatomical extent, IM histologic type, and OLGA/OLGIM stage (detailed below) were recorded. Although EGD surveillance schedules were determined by the endoscopist, these generally followed the published Chilean guideline recommendations for CAG and IM endoscopic surveillance—namely, surveillance annually for OLGA III/IV, IND, or LGD, every 3 years for OLGA I/II and every 5 years if OLGA 0 with persistent *H. pylori* infection.²¹

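### Cohort entry depends partly on the outcome: a later EGD without USSBP biopsies qualifies only if it shows HGD/GA, and no indication is required

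*Combined protocol and SAP*

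**What the plan says.** All the entry rules stand under Study design and settings in the combined protocol and SAP.

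- Baseline: patients were eligible if they "had at least one non-urgent outpatient EGD with gastric biopsies collected following the USSBP between June 2015 and June 2021".
- Entry: "Participants were included in the cohort if they underwent a subsequent" surveillance EGD.
- Timing of that EGD: "In order for the subsequent EGD to qualify as surveillance, it needed to occur at least 6 months after the baseline EGD".
- Biopsies: it must also "include gastric biopsies collected according to the USSBP".
- Exception: "one exception to the USSBP requirement was if HGD or GA was detected on the surveillance (i.e. non-baseline) EGD".

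The non-urgent outpatient condition is attached to the baseline EGD only. Guideline intervals are described as what endoscopists generally followed, not as a rule for inclusion.

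The Statistical Analysis Plan section expresses the primary result as HGD/GA incidence per 100 person-years by OLGA/OLGIM group. Time runs from the baseline EGD to the earliest of the last surveillance EGD, HGD/GA or death. Patients with no qualifying later EGD are described at baseline and contribute no time. The Introduction adds an exploratory aim: "we also evaluated the stage of GA among those enrolled in endoscopic surveillance".

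**The concern.** A return EGD decides who is in the denominator, and one of its two conditions is relaxed only for patients who have the outcome. Take two patients who never came back for surveillance. Each has an EGD years later because of symptoms, with targeted biopsies only. The one with cancer enters and brings an event; the one with a benign finding does not enter and brings no time. Non-returners with no later EGD bring no time either.

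Two results are exposed. The primary incidence rates gain events without the matching person-time. The GA-stage description, the analysis closest to the title's question about the impact of surveillance, combines cancers found by planned surveillance with cancers that declared themselves by symptoms. The plan neither separates the two nor includes a sensitivity analysis on the point.

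**Working it through.** The documents give no sample size, event count, return rate or mode of detection, so there is no stated figure to reproduce. The checks below concern direction and possible size.

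**1. Who enters, from the text.** For a non-returner with a symptom-driven EGD at least 6 months after baseline:

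| Biopsies at that EGD | HGD/GA found | Benign |
|---|---|---|
| USSBP | enters | enters |
| Not USSBP | enters (exception) | stays out |

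The asymmetry lies in the second row. The absence of a setting or indication rule is neutral to outcome by itself; it lets symptom-driven EGDs reach that row.

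**2. Direction, from the dates.** The longest possible follow-up, from 1 June 2015 to 6 March 2023, is about 7.76 years. A patient who enters through a cancer-detecting EGD adds one event in at most 7.76 person-years: 100 / 7.76 = 12.9 per 100 person-years or more. Such an entry raises any group rate below that level.

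**3. Sensitivity to a few cases (assumed).** Start from 20 events in 3,500 person-years, 0.57 per 100, and add cases at 2 person-years each:

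| Added | Rate per 100 person-years | Share of events |
|---|---|---|
| 3 | 23 / 3,506 = 0.66 | 13% |
| 5 | 25 / 3,510 = 0.71 | 20% |
| 10 | 30 / 3,520 = 0.85 | 33% |

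The plan itself expects few primary events.

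**4. Possible size (assumed).** Take 1,000 returners followed for 4 years at a true 0.30 per 100 person-years, which gives 12 events in 4,000 person-years. Let there be k non-returners per returner with the same hazard. Let a share c of their cancers be captured by a symptom-driven EGD, each with 3 person-years:

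rate = (12 + 12kc) / (4,000 + 3 × 12kc)

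- k = 0.5, c = 0.1: 12.6 / 4,001.8 = 0.31 per 100, or 1.05 times the true rate.
- k = 2, c = 0.5: 24 / 4,036 = 0.59 per 100, or 1.98 times.
- k = 2, c = 0.5, non-returners' hazard halved: 18 / 4,018 = 0.45 per 100, or 1.49 times.

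**5. Second model (assumed).** With a return fraction r and a captured share q, observed/true is approximately 1 + q(1 − r)/r. An exact constant-hazard version, at a true 0.5 per 100 person-years and 3.5 years of follow-up, gives:

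| r | q = 0.25 | q = 0.5 |
|---|---|---|
| 0.9 | 1.03 | 1.06 |
| 0.7 | 1.11 | 1.21 |
| 0.5 | 1.25 | 1.49 |
| 0.3 | 1.58 | 2.15 |

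At q = 0 the ratio is 1.00. Both models let no benign symptom-driven EGD qualify and lose no cancers to other providers; either would lower the ratios.

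**The case against.** The strongest reply is that the net direction is unknown. The health system is open, so cancers diagnosed elsewhere are missed, which lowers the rate. That stands. A reader might infer that published incidence must be inflated; the documents support only an upward push from this one selection, of unknown size.

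A reader might also infer that the missing non-urgent outpatient condition is the defect, and that imposing it on follow-up EGDs would cure it. It would not. A benign urgent EGD with USSBP biopsies already qualifies, and a symptomatic patient can have a scheduled outpatient EGD. Setting is only a proxy for indication. As a primary definition, such a rule would also discard confirmed events while keeping baseline-to-return time in which they could not be counted.

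Nor do the documents support removing every symptomatic cancer. An interval cancer in a patient already in the cohort is a true incident event and belongs in the rate.

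Distortion of the OLGA/OLGIM comparison is a further tempting inference. The guideline intervals differ by stage, so the share of symptom-driven entries could differ too, but nothing in the documents shows that it does or which way a hazard ratio would move.

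Two smaller points stand. GA stage is labelled exploratory and has no planned test. Supplementary Figure 1 and the supplementary methods were not available for this review, so an indication filter there cannot be excluded, although the text cites the supplementary methods only for biopsy sampling and autoimmune gastritis.

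**Conclusion.** The point holds as a matter of outcome-dependent entry. As written, the rule admits some non-returners because they have HGD/GA and excludes otherwise similar patients because they do not. This pushes the rate upward and leaves the GA-stage result a mixture of modes of detection.

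The ranges of 1.05 to 1.98 and 1.03 to 2.15 rest wholly on assumed return fractions, capture shares, hazards and follow-up, and are not estimates for this cohort. If no patient entered only in this way, the effect is nil. Net bias is not established. This is a cheap improvement to the analysis, not a reason to replace the primary definition.

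**What to change.** Keep the current primary definition and add three things.

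1. Classify each follow-up EGD from existing records as planned surveillance or symptom-driven. Where indication is not recorded, use urgent or inpatient versus non-urgent outpatient as a stated proxy.
2. Repeat the incidence rates and the Cox and Poisson models without patients whose only qualifying follow-up EGD was symptom-driven, or qualified only through the HGD/GA exception. Keep interval cancers in patients who had already entered. For this selection, read the result as a lower bound, because the time from baseline to the return EGD cannot contain the excluded events. Alternatively, start follow-up at the first qualifying return EGD; events found at that EGD then no longer count.
3. Report GA stage separately by mode of detection, with the number of patients in each category.

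The cost is some chart review, since the plan says endoscopic findings were abstracted from procedure reports but not that indication or urgency was recorded at follow-up. The sensitivity analysis will also have fewer events and wider intervals. No new patients or procedures are needed.

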presence or absence of CAG/IM and to provide a corresponding OLGIM stage.²⁵ Agreement between the pathologists for OLGA groups, OLGIM groups and IM were Kappa 0.73, 0.78 and 0.86, respectively. In all discrepant cases, an agreement was reached between the pathologists with no need for a third pathologist as an arbiter. Gastric dysplasia was categorized as IND, LGD or HGD according to the Vienna classification.²⁶ The most advanced discrete histology observed in the set of biopsies was used as the global diagnosis for analysis purposes. Antrum-restricted IM was defined as IM located only in the antrum or incisura angularis without evidence of corpus involvement, while corpus-extended IM was defined as IM located in the corpus irrespective of the findings in the antrum or incisura angularis.

Active *H. pylori* infection was determined based on Giemsa staining in any of the gastric samples. Presence of *H. pylori* at both baseline and surveillance EGD was considered as persistent *H. pylori* infection; whereas positive *H. pylori* at baseline and negative at follow-up was considered *H. pylori* eradication, as long as treatment occurred in between. Autoimmune gastritis (AIG) histologic features were also assessed and recorded (further described in supplementary methods).²⁷

Statistical Analysis Plan

Patients were categorized based on OLGA and OLGIM stage as low-risk (OLGA/OLGIM 0-I), intermediate-risk (OLGA/OLGIM II) and high-risk (OLGA/OLGIM III-IV).¹⁵⁻¹⁸ Demographic and clinical characteristics were compared between the OLGA/OLGIM groups. Categorical variables were expressed as percentages (%) and continuous variables were expressed as mean and 95% confidence interval (95%CI) or median and interquartile range (IQR) as appropriate. The Chi-square test was used to compare categorical variables and differences in continuous variables were evaluated with t-test or Mann-Whitney U test, as appropriate.

For the primary analysis, we analyzed the rate of progression to HGD/GA in each of the defined OLGA/OLGIM groups, expressed as incidence rate per 100 person-year with 95%CI. Also, given that OLGA/OLGIM II is potentially an intermediate-risk category,¹⁵⁻¹⁸ we conducted a subgroup analysis evaluating factors associated with progression of OLGA II vs. OLGA 0/I. For the models

evaluating cumulative HGD/GA risk, follow-up time started at the baseline EGD and continued until the earliest of the following: last available surveillance EGD, occurrence of HGD/GA or death. Cumulative risk of the composite primary outcome was estimated from Kaplan-Meier functions.

Univariate and multivariable Cox proportional hazards models were used to assess factors associated with HGD/GA, expressed as hazard ratio (HR) and 95%CI. Given the expected low number of primary outcome events (HGD/GA), Poisson regression models were used as a sensitivity analysis to estimate the adjusted incidence rate ratio (aIRR) by OLGA and OLGIM staging. Separate models for OLGA and OLGIM staging were performed, given the high correlation and collinearity of these variables. Models were adjusted for age, sex, active *H. pylori* infection, and the number of surveillances EGDs during the study period.

Secondary analyses included 1) differences in progression to HGD/GA based on anatomic extent and IM subtype, according to the following subgroups: antral-restricted complete-type IM, antral-restricted incomplete-type IM, corpus-extended complete-type IM and corpus-extended incomplete-type IM, using the log-rank test for equality survival function. Patients with unavailable IM histological subtype were excluded from these analyses (i.e. “IM unavailable, 10.9%”); 2) change in a global histological category with respect to either histopathological progression or regression; 3) changes in OLGA and OLGIM stages during the follow-up. Multivariable logistic regression analyses, adjusted for age, sex and *H. pylori* infection, were used to evaluate factors associated with histopathological or OLGA/OLGIM progression and regression (binary outcome), and expressed as adjusted odds ratios (aOR) and 95%CI. We also evaluated the stage of GA among patients enrolled in endoscopic surveillance.

As an exploratory analysis, we characterized the demographic and histopathological characteristics of those patients who had baseline EGD with USSBP but who did not undergo subsequent surveillance EGD (and thus did not meet inclusion criteria for the primary analytic cohort).

An *a priori* two-sided p-value threshold of 0.05 was established for statistically significant results. All statistical analyses were conducted using STATA v14.2 (Statacorp, College Station, TX, USA).

REFERENCES

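### The plan compares continuous characteristics across three ordered OLGA/OLGIM risk groups but names only two-sample tests for them

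*Combined protocol and SAP*

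**What the plan says.** All of the relevant text is in the Statistical Analysis Plan section of the combined protocol and SAP.

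- **Groups.** Patients are classed as "low-risk (OLGA/OLGIM 0-I), intermediate-risk (OLGA/OLGIM II) and high-risk (OLGA/OLGIM III-IV"). The classification is made once with OLGA and once with OLGIM.
- **Comparison.** "Demographic and clinical characteristics were compared between the OLGA/OLGIM groups".
- **Tests.** "The Chi-square test was used to compare categorical variables", and "differences in continuous variables were evaluated with t-test or Mann-Whitney U test, as appropriate".
- **Threshold.** A "two-sided p-value threshold of 0.05 was established for statistically significant results".

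The section names no ANOVA, Kruskal-Wallis or trend test. It gives no list of pairs, no rule for merging groups and no multiplicity adjustment.

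**The concern.** The comparison is between three groups, but a t-test or a Mann-Whitney U test compares two. The qualifier at the end of the test sentence does not help, because it only chooses between two tests with the same limit. The Chi-square test named beside them handles three groups in one test, so the gap is confined to continuous variables.

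An analyst would have to improvise by testing all three pairs, testing some of them, or merging groups. These routes can give different p-values for the same variable, and the plan does not choose among them. Running several pairs without adjustment raises the chance of a spurious difference. Testing pairs separately also makes no use of the ordering of the groups.

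What is at stake is the description of the study's main exposure groups. Readers will use the comparison of age, and of any other continuous characteristic, to judge how the low-, intermediate- and high-risk groups differ.

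**Working it through.** **Inputs from the documents.** There are three groups per staging system, the threshold is two-sided 0.05, and the tests are the t-test or Mann-Whitney U. The 0.05 is declared and not derived, so there is no plan figure to reproduce. As a check, one two-sample t-test at 0.05 has a simulated size of 0.049-0.051, as it should.

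**Assumed inputs.** The documents give no group sizes, so a range of sizes was used. Every figure below is for one continuous variable and one staging system, with no true difference between any of the groups (the global null).

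**Step 1: all three pairs, equal groups, large samples.** At least one pair is significant when the studentized range of the three means exceeds √2 times the two-sided critical value:

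P(Q₃ > √2 × 1.96) = 0.122

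With 27 degrees of freedom the result is 0.119. Treating the tests as independent gives 1 − 0.95³ = 0.143. That is too high, because the three pairs share groups.

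**Step 2: t-tests by simulation, 200,000 runs per row.** Two pairs means the first group against each of the others. One pair means the first group against the second.

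| Assumed sizes | Three pairs | Two pairs | One pair | One-way ANOVA | ANOVA, then unadjusted pairs only if significant |
|---|---|---|---|---|---|
| 100/100/100 | 12.3% | 9.0% | 5.0% | 5.0% | 5.0% |
| 30/30/30 | 12.2% | 9.0% | 5.0% | 5.0% | 5.0% |
| 600/200/100 | 12.0% | 9.8% | 5.1% | 5.1% | 5.1% |
| 700/100/50 | 11.5% | 9.6% | 5.0% | 4.9% | 4.9% |
| 800/150/50 | 11.6% | 9.8% | 5.0% | 5.0% | 5.0% |
| 900/50/30 | 11.6% | 9.7% | 5.0% | 4.9% | 4.8% |
| 450/450/20 | 10.8% | 9.6% | 4.9% | 5.0% | 4.9% |

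The simulation error for the three-pair column is about √(0.12 × 0.88 / 200,000) = 0.0007, or 0.07 percentage points.

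**Step 3: Mann-Whitney, three pairs, 10,000 runs.** The result is 12.1% with 100 per group and 11.6% with 350/100/50.

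**Step 4: after the change.** One three-group test per variable holds about 5%, as the ANOVA column shows. Pairwise tests run only after a significant ANOVA also stay at about 5% under the global null. If only one pair of groups is truly equal, only one true null hypothesis can be falsely rejected, and it is tested at 5%. With three groups, this sequence therefore controls the familywise error without further adjustment. The alternative is Bonferroni at 0.05/3 = 0.0167 per pair, which is at most 3 × 0.0167 = 0.05 in total.

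**The case against.** The strongest reply is that the plan is under-specified here and not demonstrably in error. Several parts of that reply stand.

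- **The threshold.** A reader might infer that the comparisons run at about 12% in place of a promised 5%. The documents do not support this. The 0.05 is a threshold for each result, no familywise rate is stated, and each pairwise test at 0.05 meets the threshold. Nor does the plan say that all three pairs are tested.
- **Merging groups.** A reader might also infer that no two-sample route is valid. Merging three groups into two by a fixed rule and running one test does hold 5%, and merging adjacent groups respects their order. The weaker objection is that it drops the plan's own three-level classification and that no cut is named.
- **Two-group uses.** The test sentence has legitimate uses, because the plan names a "subgroup analysis evaluating factors associated with progression of OLGA II vs. OLGA 0/I". Two-sample tests could serve for describing those two groups.
- **Outcome results.** The primary analysis reports progression "expressed as incidence rate per 100 person-year with 95%CI", and "Univariate and multivariable Cox proportional hazards models were used to assess factors associated with HGD/GA". Kaplan-Meier, Poisson, log-rank and logistic methods cover the rest. Age enters the models as a listed covariate, and the plan describes no selection of covariates from these descriptive p-values.

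The mismatch itself survives. The plan states a three-group comparison, and nothing in the documents supplies a three-group test for continuous variables.

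**Conclusion.** The point holds in a limited form, and its severity is minor. The tests named for continuous characteristics do not fit the three-group comparison they are meant to serve.

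The size depends on what was done. The chance of at least one false positive is about 11-12% if all three pairs are tested unadjusted, 9-10% if two are, and 5% if one is. These figures apply per variable and per staging system, under the global null and with assumed group sizes.

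Only descriptive comparisons of continuous characteristics are affected. It would be tempting to carry the concern over to the HGD/GA findings, but the plan uses neither test in its primary or secondary outcome analyses, so those are untouched.

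**What to change.** Replace the sentence on continuous variables with wording to this effect: continuous characteristics are compared across the three OLGA groups, and separately across the three OLGIM groups, by one-way ANOVA or Kruskal-Wallis, or by a trend test because the groups are ordered. Pairwise t-tests or Mann-Whitney U tests are reported only after a significant three-group test, or with a multiplicity adjustment such as Holm or Bonferroni. The two-sample tests are kept for true two-group contrasts, such as OLGA II against OLGA 0/I.

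The cost is one sentence and a re-run of a few descriptive p-values, some of which may become slightly less favourable. No outcome analysis needs to change.
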